### **Screening baseline procedures**

Assessments performed exclusively to determine eligibility for this study will be done only after obtaining informed consent. Assessments performed for clinical indications (not exclusively to determine study eligibility) such as COVID testing may be used for baseline values even if the studies were done before informed consent was obtained.

All screening procedures must be performed within 7 days prior to registration unless otherwise stated. The screening procedures include:

- 1 Informed Consent
- 2 Medical history: Complete medical and surgical history
- 3 Demographics: Age, gender, race, ethnicity
- 4 Review subject eligibility criteria
- 5 Review previous and concomitant medications
- 6 Adverse event assessment

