We will analyze the efficacy of RPS in relation to the primary outcome of hospitalization. If there is a significant difference between the two arm with p-value of <0.01, we will not continue the study. For data quality and integrity, we will also analyze the efficacy of RPS in relation to the secondary outcomes of TTCA and symptom severity score to assess efficacy and ensure no increase in harm in the intervention arm.

**Section 14. Statistical Considerations:** Describe the statistical analyses that support the study design.

**Study design/Study outcomes measures:** We will conduct a double-blinded, randomized clinical trial comparing RPS (~20g twice daily for 14 days) with placebo (non-resistant starch) in 1500 adults (age  $\geq 18$  years old) with COVID-19 diagnosis (defined by a positive swab) who are being managed in the outpatient setting. The primary outcome is hospital admission due to COVID-19 related complications. The secondary outcomes are TTCA and symptom severity score. We also will investigate some exploratory outcomes such as ER visits without admission, and among those hospitalized, we will explore differences in oxygen requirement, need for mechanical ventilation, duration of ventilation, length of hospital stay, levels of inflammatory markers routinely ordered as part of clinical care (CRP, LDH, D-dimer, Ferritin, IL-6), and rates of discharge between the RPS and placebo arms.

**Sample size and accrual:** Assuming a 14% admission rate in the placebo group, we calculated that a sample size of 1362 (we will enroll 1500 to account for 10% loss to follow up) will be required to provide 80% power (with a two-sided alpha level of 0.04 to detect an absolute reduction in hospital admission rates of 5% or more in the RPS group. **The primary analysis will be based on the intention-to-treat principle, with all patients included in their assigned group.**

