For our secondary outcomes, assuming a TTCA of about 14 days in the placebo group with standard deviation of 5 days, we calculated that a sample size of 196 would be required to provide 80% power (with a two-sided alpha level of 0.05) to detect an absolute reduction in TTCA by 2 days or more in the RPS group. For the outcomes of symptom severity score, we assumed that the placebo group would have a peak score of 20 with a standard deviation of 5 points, and we calculated that a sample size of 32 patients would be required to provide 80% power (with a two-sided alpha level of 0.05) to detect an absolute reduction in symptom severity score of 5 points or more in the RPS group.

Total accrual between all sites is 1500 patients. Depending on accrual rates, some sites may accrue more than other sites with a total goal of 1500 patients.

**Data analysis plan:** The primary outcome of hospital admission rates will be compared with the use of Pearson's chi-square test. The secondary outcomes of TTCA and symptom severity score will be compared in the two groups by means of a two-sample t-test. Adjusted measures and subgroup effects for the primary and secondary outcomes will be analyzed with the use of logistic regression and linear regression, respectively. Generalized estimating equations and linear mixed models will be used to test for an interaction between treatment group and

site in primary and secondary outcomes, respectively. The alpha level will be set at 0.05 for all analyses, 95% confidence intervals will be calculated, and all comparisons will be two-tailed.

*Interim analysis plans:*

Once our enrollment target for the secondary outcomes is reached (n~200), we will perform an interim analysis to assess safety, feasibility and treatment effect.

*Interim analysis 1(safety):*

All adverse events will be summarized and the independent data safety monitoring committee (DSMC) will make recommendations regarding continuation of recruitment. None of the DSMC members will be on our IRB protocol or the study team.

*Interim analysis 2 (feasibility):*

Study enrollment, follow up and any withdrawals from the study will be summarized and discussed by IDSMC to see if the degree of missing data is acceptable and if any further efforts need to be taken to optimize enrollment and follow up. Successful feasibility will be defined as more than 60% of patients took at least 50% of their prescribed doses (as directed by study team).

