#### **SECTION IV: PROTECTION OF RESEARCH SUBJECTS**

**Confidentiality & Security of Data:**

1. What protected health information (medical information along with the HIPAA identifiers) about subjects will be collected and used for the research? We will need subjects' demographics such as age, sex, race, height, weight, and BMI.
2. How will the research data be collected, recorded and stored? We will store all data on the protected/secure/encrypted Yale G drive/server. Other sites will send collected data securely via Yale secure file transfer.
3. How will the digital data be stored? Yale desktop computer.
4. What methods and procedures will be used to safeguard the confidentiality and security of the identifiable study data and the storage media indicated above during and after the subject's participation in the study? All information will be stored on a secured Yale drive. No personal laptops or computers will be used to store any of this information.

All portable devices must contain encryption software, per University Policy 5100. If there is a technical reason a device cannot be encrypted please submit an exception request to the Information Security, Policy and Compliance Office by clicking on url <http://its.yale.edu/egrc> or email [[contact]](mailto:[contact])

5. What will be done with the data when the research is completed? Are there plans to destroy the identifiable data? If yes, describe how, by whom and when identifiers will be destroyed. If no, describe how the data and/or identifiers will be secured.

This information will be kept for five years. After that time it will be destroyed or de-identified, meaning we will replace the identifying information with a code that does not directly identify the participant. The principal investigator (PI) will keep a link that identifies the participant to the coded information, but this link will be kept secure and available only to the PI or selected members of the research team. Any information that can identify the participant will remain confidential. The research team will only give this coded information to others to carry out this research or to investigators approved for use of banked data.

6. If appropriate, has a Certificate of Confidentiality been obtained? NA

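### The primary test is an unadjusted chi-square although age and co-morbidities are recorded at entry: a valid analysis that leaves some precision unused

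*Combined protocol and SAP*

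**What the plan says.** The Data analysis plan in Section 14 sets the primary comparison: "The primary outcome of hospital admission rates will be compared with the use of" Pearson's chi-square test. It then adds a second layer: "Adjusted measures and subgroup effects for the primary and secondary outcomes will be analyzed with the use of logistic regression and linear regression", respectively. No covariate is named for that adjusted analysis, and nothing makes it the basis of the primary conclusion. Site enters only through a separate test of treatment-by-site interaction. Under Randomization, allocation is stratified by site and by nothing else.

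On baseline data, the list under Screening baseline procedures includes "Demographics: Age, gender, race, ethnicity" and a full medical and surgical history. Table 4 (Time and Events) marks assessment of co-morbidities at enrollment. The date of the positive test has to be known, because the four-month follow-up is counted from it (Duration of Follow-Up). BMI appears only in Section IV, Confidentiality & Security of Data, among "demographics such as age, sex, race, height, weight, and BMI". No time point is attached, and neither BMI, height nor weight is in the screening list or in Table 4.

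**The concern.** Eligibility has no upper age limit and excludes few co-morbidities, so baseline risk of a COVID-19 admission plausibly varies widely between participants. An unadjusted test treats that variation as noise. A standardized risk difference from a covariate-adjusted model estimates the same absolute reduction on which the trial was sized, usually with a smaller standard error. It also removes the influence of a chance imbalance in age or co-morbidity, which stratification by site does not prevent.

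The trial is sized at its 80% target with no reserve, so precision that costs no patients has some value. Leaving the covariates of the planned adjusted analysis unnamed has a further cost: they could be chosen after the data are seen, and the adjusted result could then compete with the chi-square.

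**Working it through.** **Inputs from Section 14, Sample size and accrual.** "Assuming a 14% admission rate in the placebo group"; power "to detect an absolute reduction in hospital admission rates of 5% or more in the RPS group", hence 14% against 9%; 80% power; two-sided alpha 0.04; N = 1362, with 1500 enrolled for 10% loss. The allocation ratio is not stated, and 1:1 is assumed.

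**Step 1: reproduce the stated N.** Pooled-variance formula for two proportions, without continuity correction:

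n per arm = [z(0.98)·√(2·p̄·(1−p̄)) + z(0.80)·√(p1(1−p1) + p2(1−p2))]² / (p1−p2)²

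With p̄ = 0.115: [2.054·√0.2036 + 0.842·√0.2023]² / 0.05², rounded up to 682 per arm, or 1364 in total against 1362 stated. The figure reproduces. Chi-square power at 1362 is 80.0% at alpha 0.04 and 82.5% at alpha 0.05. After 10% loss from 1500, 1350 remain, with 79.6% power at alpha 0.04; that shortfall is immaterial.

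**Step 2: events available for a model.** 681 × 0.14 + 681 × 0.09 = 95 + 61, about 157. This is enough for a few prespecified covariates.

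**Step 3: gain from adjustment.** The documents give no prognostic strength, so the c-statistic of the baseline covariates is an assumption, shown over a range. Let R² be the share of outcome variance that the baseline score explains. Adjustment then acts roughly like a sample of N/(1−R²), and the N giving unchanged power is about N·(1−R²). For c = 0.75, 1362/(1−0.1009) = 1515 effective patients, and 1362 × (1−0.1009) = 1225.

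The simulated columns come from 6000 trials per row at N = 1362 and two-sided alpha 0.04. They compare the chi-square with the Wald test of treatment in a logistic model that includes the score. Monte Carlo error is about 0.5 point.

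| Assumed c | R² | Analytic power, adjusted (unadjusted 80.0%) | Simulated: chi-square → adjusted | N for 80% power |
|---|---|---|---|---|
| 0.60 | 0.013 | 80.5% | 80.6% → 80.7% | 1344 |
| 0.65 | 0.031 | 81.3% | 80.5% → 81.9% | 1319 |
| 0.70 | 0.060 | 82.4% | 79.5% → 81.7% | 1281 |
| 0.75 | 0.101 | 84.1% | 79.3% → 84.0% | 1225 |
| 0.80 | 0.158 | 86.5% | 80.5% → 87.0% | 1146 |
| 0.85 | 0.237 | 89.6% | 80.7% → 90.4% | 1039 |

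A separate simulation of the standardized risk difference itself (influence-function standard error, 675 per arm, 4000 trials per setting) agrees: 81.2% → 81.8% at c = 0.64, 80.5% → 83.0% at 0.70, 80.6% → 84.9% at 0.75, and 81.2% → 87.2% at 0.80.

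**Step 4: type I error at the final analysis.** At c = 0.75 under the null (4000 trials), the adjusted logistic test rejected in 3.9% against a nominal 4%. The standardized risk difference gave 3.5% to 4.5% across its settings.

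**Step 5: type I error at the interim look.** At about 200 patients, expected events are 100 × 0.14 + 100 × 0.09 = 23. With 100 per arm, five covariates and 12,000 null trials, the standardized risk difference with influence-function standard error rejected in about 1.4% at the nominal 0.01; the chi-square rejected in 1.0%. The Monte Carlo standard error is √(0.01 × 0.99/12000) = 0.09 point, so the excess is real, though mild.

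**The case against.** The strongest reply is that nothing here is wrong. The chi-square is valid for a randomized binary outcome, the sample size was built for exactly that comparison, and the stated N reproduces. This stands. A reader might infer that the primary analysis is defective or the trial underpowered; the documents do not support that.

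Second, adjustment is already in the plan, and a chance imbalance would be examined there. This stands in part: the plan does foresee adjustment, but not as the primary analysis and without named covariates. As written, the logistic model would also yield a conditional odds ratio and not the absolute difference used for sizing.

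Third, a reader might infer that BMI is available at entry for everyone. The documents do not show this. BMI is mentioned only in the confidentiality section, and all contact is by phone and health record, so its completeness is unknown. Nor is a co-morbidity count or instrument defined; one has to be written.

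Fourth, the size of the gain is assumed, and the simulations in the table used one correctly specified, fully observed score, which is favourable. A run with five estimated covariates at 1350 patients gave gains of about 1.5 to 2.5 points at moderate strength, so estimating the model costs little, but the gain stays modest.

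Fifth, it is tempting to say that adjustment preserves type I error throughout. It does so at the final analysis but not, in Step 5, at the interim look. That objection stands and shapes the fix.

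**Conclusion.** The point holds as a missed efficiency. The primary test uses no patient-level prognostic information, although age and co-morbidities are recorded before treatment and regression adjustment is already foreseen.

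The gain at the final analysis is about 1 to 2.5 points of power if the covariates reach a c-statistic of 0.65 to 0.70, and about 4 to 6 points or slightly more at 0.75 to 0.80. At 0.60 it is negligible. At 0.70 to 0.80 the equivalent saving in patients is about 6% to 16%. These figures rest on an assumed prognostic strength, 1:1 allocation, rates of 14% and 9%, and alpha 0.04. Under the 0.05 in the Data analysis plan, the unadjusted test already has 82.5% power. The change is worth making because it is cheap, not because the present analysis fails.

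**What to change.** Amend the Data analysis plan so that the final primary analysis is a standardized (g-computation) risk difference. Fit a logistic model on treatment, site, age and a prespecified co-morbidity count. Predict each participant's risk under both arms and average the difference over all participants. Use an influence-function or bootstrap standard error. Days from positive test to randomization may be added. Include BMI only if the sponsor confirms that it is captured before randomization. Define the co-morbidity count and a rule for missing baseline values, such as mean imputation, before unblinding.

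State one final alpha after reconciling the 0.04 in Sample size and accrual with the 0.05 set for all analyses in the Data analysis plan. Keep the Pearson chi-square as the test at the interim look near 200 patients, and report it at the end as a sensitivity analysis.

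The cost is analysis-plan wording and a few lines of code. No additional patients are needed, and no new data as long as BMI is confirmed or left out.

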**Secondary Outcome Measure:**

TTCR will be defined as a return to normal body temperature to 97°F -99°F as reported by the patient, and resolution of any major presenting symptoms (myalgia, cough, shortness of breath, GI symptoms) maintained for 72 hours.

-To assess the effect of RPS on symptom severity score

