| Adverse events related to
Resistant Potato Starch (RPS) | 
 
• Allergy to potato or corn based starch
 
• Persistent* Abdominal cramping or pain
 
• Nausea or vomiting
 
• Diarrhea
 
• Persistent Bloating
 
• Persistent Flatulence
 
 | All will be reported within 1 to 5 days to safety monitoring coordinator of event becoming known to PI at each site. |
|--|--|--|

\*Persistent symptoms will be defined as lasting 72 hours or longer

- If persistent side effects related to the investigational agent occur, a dose reduction can be made to once daily instead of twice daily dosing at the discretion of the PI or Co-I. If intolerance continues, despite decreasing the frequency of dosing, the investigational agent may be held for up to 3 days. Investigational agent can also be held for up to 3 days if the patient is unable to take oral intake for any reason. If investigational agent is held longer than 3 days, subject will be removed from treatment and included with an intention to treat protocol.
- The study intervention will be discontinued if patient meets the primary study endpoint of hospitalization

The Placebo uses corn starch. A potential risk although rare is allergy to corn. We will in screening ask about the potential subjects' exposure to corn and any reaction or avoidance of corn. Allergies to corn are extremely rare and there are no recent literature documenting specific rates, but one study from 1950 showed a very low rate of 0.16% (DOI:[https://doi.org/10.1016/0021-8707\(50\)90098-0](https://doi.org/10.1016/0021-8707(50)90098-0)).

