**Off Treatment Criteria**

Patients will be removed from protocol therapy when any of the criteria listed above. The reason for ending protocol therapy and the date the patient was removed from treatment will be documented. All patients who discontinue treatment should comply with protocol specific follow-up procedures. The only exception to this requirement is when a subject withdraws consent for all study procedures or loses the ability to consent freely.

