### **Subject Replacement**

If subject needs to go off study after randomization, protocol dictates that subject cannot be replaced given the intention to treat nature of the protocol.

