### **Procedures during treatment and follow up procedures**

*Assessment for primary objective of hospitalization at one month via phone and EHR:*

Every 2 days phone questionnaires (**see attached questionnaire**) and EHR review for the first 14 days followed by once weekly phone call and EHR review to complete a month follow up from last dose of treatment.

*Assessment for secondary objectives of TTCA and symptom severity score via phone and EHR:*

Every 2 day phone questionnaires (**see attached questionnaire**) and EHR review for the first 14 days followed by once weekly phone call and EHR review to complete a month follow up from last dose of treatment.

*Assessment of exploratory objectives*

EHR review to complete 4 months follow up from COVID positive test

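### Time to clinical recovery is analysed by t-test with no value or censoring rule for patients without an observed recovery; the effect shows mainly at the interim

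*Combined protocol and SAP*

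**What the plan says.** - **Method.** Section 14, Data analysis plan: "The secondary outcomes of TTCA and symptom severity score will be compared in the two groups by means of a two-sample t-test". Adjusted and subgroup effects for the secondary outcomes use linear regression. No survival method appears.
- **Definition.** Section 4, Secondary Outcome Measure: "TTCR will be defined as a return to normal body temperature to 97°F -99°F as reported by the patient", together with resolution of major symptoms, held for 72 hours. No time origin is given, and there is no value for a patient who does not reach this state.
- **Sample size.** Section 14 sizes the outcome at 196 in total, "assuming a TTCA of about 14 days in the placebo group with standard deviation of 5 days", for a 2-day reduction. The primary outcome has a loss allowance ("we will enroll 1500 to account for 10% loss to follow up"); the 196 has none.
- **Who is followed.** Off Treatment Criteria: "All patients who discontinue treatment should comply with protocol specific follow-up procedures". The follow-up procedures section plans "Assessment for secondary objectives of TTCA and symptom severity score via phone and EHR", every 2 days to day 14 and then weekly to 30 days after the last dose.
- **Intention to treat.** A patient held off the agent too long is handled thus: "subject will be removed from treatment and included with an intention to treat protocol". Subject Replacement says a "subject cannot be replaced given the intention to treat nature of the protocol". The explicit intention-to-treat sentence in Section 14 concerns the primary analysis.
- **Interim.** Sections 13 and 14 trigger it when enrolment reaches about 200. TTCA is analysed there for efficacy and to check for harm. The only stopping threshold, p < 0.01, applies to hospitalization.

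**The concern.** TTCR is a time-to-event outcome. A patient who dies, drops out or is still ill at the data cut has no recovery time, and a t-test or linear model can only leave that patient out unless a rule supplies a value. The primary outcome has a rule for death; TTCR has none. Loss to follow-up appears only as a reason for leaving the study.

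At a data cut soon after enrolment, the completed recoveries come disproportionately from fast recoverers in both arms. That compresses the difference between arms and discards the information that the other patients were still ill after a known number of days. The monitoring committee would then see a smaller and less precise effect than the data support. Without a rule, the choice of who counts is also left until data are in hand.

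**Working it through.** **1. The plan's figure reproduces.** Inputs from Section 14: difference 2 days, SD 5, two-sided alpha 0.05, power 80%; 1:1 allocation assumed. Total N = 4 × [5 × (1.960 + 0.842) / 2]² = 196.2, against 196 stated. This treats TTCR as a fully observed continuous outcome.

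**2. Final analysis.** The phone window ends at about day 14 + 30 = 44. With a placebo mean of 14 and SD of 5, the share unrecovered at day 44 is 1 − Φ((44 − 14)/5) = 1 − Φ(6), effectively zero; a lognormal with the same mean and SD gives 0.03%. With 10% non-informative loss spread over the window, a simulated 2.0-day difference reads as 1.99 days.

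**3. Interim: share of recoveries complete.** The documents give neither an accrual rate nor a cut date. Assumption: 1500 patients at a constant rate over the six months in Section 1 (about 183 days) is 8.2 per day, so 200 take about 24 days. A slower case, 49 days, is half that rate. A recovery needs 3 more days for the 72-hour confirmation, so in placebo it is confirmed on average at day 17.

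For enrolment over A days and a cut w days after the last enrolment, the share complete is (5/A) × [G(b) − G(a)], where a = (w − 17)/5, b = (w + A − 17)/5 and G(x) = xΦ(x) + φ(x).

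- A = 24, w = 0: a = −3.4, b = 1.4; (5/24) × (1.437 − 0.000) = 0.30
- A = 24, w = 14: a = −0.6, b = 4.2; (5/24) × (4.200 − 0.169) = 0.84
- A = 49, w = 0: a = −3.4, b = 6.4; (5/49) × (6.400 − 0.000) = 0.65

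**4. Interim: estimate and power.** Simulated with 100 per arm, N(14, 5) against N(12, 5), whole days and 72-hour confirmation. Ranges cover repeat runs.

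| Enrolment, wait | Placebo complete (simulated) | 2-day benefit reads as | t-test power | Log-rank power |
|---|---|---|---|---|
| 24 d, none | 28% | 1.4 d | 24–26% | 44–46% |
| 24 d, 14 d | 82–83% | 1.8 d | 68–71% | 72–75% |
| 49 d, none | 64% | 1.9–2.0 d | 60–65% | 61–66% |
| 44 d wait | near all | 2.0 d | 79–80% | 74% |

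The t-test uses completed recoveries; the log-rank censors the rest at the cut. With no true effect, both tests reject in 2–3% of trials in each direction.

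**5. If admitted patients were left out.** This is not a stated plan. Take Section 14's 14% and 9% admission, the same N(14, 5) recovery in both arms, and an assumed correlation rho between recovery time and admission risk (not in the documents). The bias is 5 × rho × [φ(1.080)/0.86 − φ(1.341)/0.91] = 5 × rho × (0.2588 − 0.1784) = 0.40 × rho days against RPS. For rho of 0.3 to 1 that is 0.12 to 0.40 days. If admitted patients are followed to recovery, it is about zero.

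**6. Dating of recovery (a separate matter).** Calls become weekly after day 14, and the Appendix A form looks back 2–3 days. Under the plan's figures 50% of placebo and 1 − Φ((14 − 12)/5) = 34% of RPS recoveries fall after day 14. If recovery were dated at the call, a true 2.0 days would read as 2.4 days; with no effect the difference stays at about zero.

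**The case against.** A reader might infer that the t-test cannot be carried out, that admitted patients will be dropped, or that most recoveries must still be open at the interim. The documents support none of these.

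- A t-test runs on complete cases. Under the plan's mean and SD almost everyone has recovered by day 44, so the final comparison is close to sound. This stands.
- The follow-up and intention-to-treat wording points to keeping admitted patients in. Leaving them out is only something the text fails to rule out. This stands, and the bias in step 5 should not be presented as a consequence of the plan.
- The 1.4-day and 25% figures need fast, constant accrual and a cut on the day of last enrolment. Neither is stated, and a 14-day wait or 49-day accrual removes most of the loss. This stands.
- No stopping threshold uses TTCR, and no false signals arise under no effect. This stands, although Section 13 lists futility among the interim's purposes without giving a rule.
- With complete data the t-test (79%) matches the restricted mean (80%) and beats the log-rank (73%), so one sentence assigning values might suffice. This stands in part. Intention-to-treat wording says who is analysed, not what number to use, and any number assigned to a patient followed for only a few days would be invented. Censoring avoids that.

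**Conclusion.** The concern holds as a missing rule joined to a method that cannot use incomplete recovery times. The final analysis is little affected by end-of-window censoring or by non-informative loss, given the plan's mean and SD; a longer recovery tail would change that. The effect of deaths is not quantified, because the documents give no death rate.

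The practical consequence is at the interim and depends on accrual and cut date, both assumed here. It runs from a 2-day benefit read as about 1.4 days, with power of about 25% against 45%, down to no material difference. The direction is to understate a real benefit, not to create a false one. The point concerns a secondary outcome without a stopping rule. It should be corrected before any unblinded look, but it does not threaten the primary analysis.

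**What to change.** In Section 14, replace the t-test for TTCR with a time-to-event analysis of all randomized patients, from randomization over one common window (for example to day 44).

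- **Main comparison:** difference in restricted mean time to recovery, in days with 95% CI. Support it with Kaplan-Meier curves and a site-stratified log-rank test.
- **Rules:** admitted patients stay in with their actual recovery date. Deaths are held as not recovered to the end of the window. Lost patients are censored at last contact, and unrecovered patients at the end of the window or the data cut.
- **Interim:** censor patients not yet recovered and use the log-rank test, since a restricted mean to day 44 is out of reach when follow-up is shorter. Otherwise, review TTCR only after the 200th patient has completed the window.
- **Separately:** record the patient-reported recovery date at each call. The change of test does not cure call-dating.
- **Unchanged:** linear models for the severity score.

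The cost is SAP wording, one date field, up to two more calls for admitted patients (750 × 0.14 + 750 × 0.09, about 173 expected) and slightly more analysis work. At 98 per arm with complete data, simulated power is 79.8% for the restricted mean, 79.1% for the t-test and 73.0% for the log-rank. So 196 holds if the restricted mean decides. With the log-rank it would need restating: 98 × (2.80/2.57)² is about 116 per arm, or about 230 in total. At 675 per arm (750 less 10%) all three exceed 99%.
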